10.10.5. Home Health Visits

A home health care service may be utilized to facilitate scheduled visits per the [SOA](#). Home health visits include a healthcare provider conducting an in-person study visit at the participant's location, rather than an in-person study visit at the site. The following may be performed during a home health visit:

- Laboratory assessments;
- Vital signs;
- Others as appropriate.

10.10.6. Adverse Events and Serious Adverse Events

If a participant has COVID-19 during the study, this should be reported as an AE or SAE and appropriate medical intervention provided. Temporary discontinuation of the study intervention may be medically appropriate until the participant has recovered from COVID-19.

It is recommended that the investigator discuss temporary or permanent discontinuation of study intervention with the study medical monitor.

10.10.7. Efficacy Assessments

Please contact the sponsor should a participant need to use alternative measures for efficacy assessments. A plan will be devised in discussion with the sponsor and investigator.

10.10.8. Independent Oversight Committees

This is an open-label, non-randomized Phase 1 study. This study will not use a DMC.

10.11. Appendix 11: Detailed Dose Escalation/De-Escalation Scheme for BLRM Design

This appendix provides the details of the statistical model, the description of prior distribution of the model parameters, and sensitivity analysis. The results of the Bayesian analyses and respective dosing decisions for some hypothetical data scenarios, and a simulation study of the operating characteristics of the model could be found in the separate Technical Supplement.

10.11.1. Statistical Model

Let $\pi(d)$ be the risk of DLT for PF-07265028 given as a single agent at dose d . The dose-DLT model is logistic:

$$\text{Logit}(\pi(d)) = \log(\alpha) + \beta \log(d / d^*)$$

$d^* = 600$ mg QD and used to scale the doses of PF-07265028. Hence, $\alpha (>0)$ is the odds of a DLT at PF-07265028 d^* mg, and $\beta (>0)$ is the increase in the log-odds of a DLT by a unit increase in log-dose.

Statistical model to be used in Part 1B along with prior specifications based on currently available data is described in the separate Technical Supplementary material to this appendix.

10.11.2. Prior Specifications for Part 1A

The Bayesian approach requires the specification of prior distributions for all model parameters, which include the parameters $\log(\alpha)$ and $\log(\beta)$. A weakly informative prior was used as there were no relevant human historical DLT data available. It was assumed that model parameters will follow a BVN distribution

$$(\log(\alpha), \log(\beta)) \sim N_2(m, S)$$

with prior means $m = (m_1, m_2)$, and prior covariance matrix S composed of standard deviations s_1, s_2 and correlation cor . It was assumed that:

$$(m_1, m_2, s_1, s_2, cor) = (\text{logit}(p^*), 0, 2, 1, 0)$$

Here, p^* is the anticipated DLT rate at the scaling dose d^* . It was assumed based on pre-clinical data that DLT rate at 600 mg QD dose was 0.2.

This prior is considered to be weakly informative.

The prior distributions of the model parameters are provided in [Table 15](#). [Table 16](#) summarizes the resulting prior distribution of DLT rate derived from the prior, which is also illustrated in [Figure 1](#). Based on the available information the starting dose of 25 mg QD satisfies the EWOC criteria.

Table 15 Prior Distribution for the Model Parameters

[figure not shown]
PF-07265028 Single Agent Parameters: BVN Weakly Informative Prior			
Parameters	Means	Standard Deviations	Correlation
($\log(\alpha), \log(\beta)$)	-1.386, 0	2, 1	0

Table 16 Summary of Prior Distribution of DLT rates for PF-07265028

PF-07265028 (mg QD)*	Prior Probabilities that DLT Rate is in the Interval			Mean	Standard Deviation	Quantiles		
	[0, 0.16)	[0.16, 0.33)	[0.33,1]			2.5%	50%	97.5%
25	0.867	0.062	0.071	0.073	0.158	0.000	0.007	0.623
50	0.831	0.078	0.091	0.091	0.175	0.000	0.013	0.688
80	0.797	0.094	0.109	0.107	0.189	0.000	0.021	0.731
125	0.754	0.111	0.135	0.128	0.204	0.000	0.033	0.773
200	0.696	0.133	0.171	0.158	0.222	0.000	0.054	0.815
320	0.616	0.154	0.230	0.201	0.244	0.001	0.092	0.862
500	0.500	0.183	0.317	0.264	0.268	0.003	0.160	0.905

*Dose levels in this table are provisional and subject to change during the study.

Figure 1. Interval Probabilities

Interval probabilities of UD, TT, and OD. Note the dashed horizontal line in the TT panel displays the probability threshold that a dose must meet to be selected as the MTD, while the dashed line in the OD panel displays the probability threshold for the EWOC design.

10.11.3. Sensitivity Analysis

Despite being prespecified in the protocol, some AEs that fall into the category of DLTs may need to be considered differently. Conversely, some AEs that are not defined as a DLT per protocol should be considered by the dose escalation algorithm. Accordingly, the new concept of an “equivocal” DLT or AE is introduced: most AE/DLTs are considered “unequivocal,” but certain types of AEs/DLTs are considered to be “equivocal.”

To mitigate the risk of dichotomizing and misclassifying DLTs, the sensitivity analysis that uses those weighted equivocal DLT/AE data into the BLRM model estimation will also be performed. The BLRM model uses all the equivocal and unequivocal AE/DLT data, but the variability associated with equivocal AEs/DLTs (less interpretable) is increased. So, the model recommendations are more heavily weighted towards unequivocal data. See below

for the posterior distribution of the BLRM model parameters based on the theory of power prior.

Suppose n participants treated at dose d with m unequivocal DLTs and r equivocal DLTs/AEs, and the weight w for the equivocal data, then based on the power prior,

$$\begin{aligned} \text{Posterior}(\alpha, \beta | d, m, r, w) &\propto L(m | \alpha, \beta, d, w) \times L(r | \alpha, \beta, d, w)^w \times \text{prior}(\alpha, \beta) \\ &\propto p(\alpha, \beta, d)^m \times [1 - p(\alpha, \beta, d)]^{n-r-m} \times p(\alpha, \beta, d)^{rw} \times \text{prior}(\alpha, \beta), \end{aligned}$$

where L is the likelihood of the observed DLT data, and $p(\alpha, \beta, d)$ is the probability of DLT at dose d that is modeled by logistic regression in BLRM. To achieve the equality sign, appropriate normalizing constant is required.

The contribution of equivocal AEs/DLTs to the data (likelihood) and the Bayesian posterior estimation of the MTD are weighted; the weight parameter controls the influence and can be interpreted as a precision parameter for the equivocal AE/DLT data, similar to the scale parameter in the power prior for the Bayesian historical borrowing.

The weight for an equivocal DLT is decreased (eg, 1 decreased to 0.5) and the weight for an equivocal AE (non-DLT by protocol) is increased (eg, 0 increased to 0.5). To maintain the integrity of a trial, the weight is pre-specified as 0.5 in the analysis. If all the investigators and the sponsor agree on the equivocal DLT/AE data, the DLT weighting approach could be the primary dose escalation method. This DLT weighting approach provides a flexible and powerful tool that may incorporate the clinician's valuable experience with some specific DLTs/AEs and improve MTD estimation in dose-escalation trials.

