The number of participants in Part 1 dose escalation of the trial may be approximately 60. The trial for Part 1A and Part 1B will be stopped when the following criteria are met:

At least 6 participants have been treated at the MTD/RDE.

The dose \tilde{d} satisfies one of the following conditions:

- *The probability of target toxicity at dose \tilde{d} exceeds 50%, ie, $\Pr(0.16 \leq \pi_{\tilde{d}} < 0.33) \geq 50\%$.*
- *A minimum of 12 participants have been treated for Part 1A, or a minimum of 9 participants have been treated for Part 1B.*

To mitigate the risk of dichotomizing and misclassifying DLTs, a sensitivity analysis that uses weighted DLT/AE data (in equivocal cases) into the BLRM model estimation will also be performed. If all the investigators and the sponsor agree on the equivocal DLT/AE data, the DLT weighting approach could be the primary dose escalation method.

Decision Rules for Part 2 Dose Expansion:

The main objective is to evaluate the RDE for PF-07265028 in combination with sasanlimab for safety and preliminary efficacy. Summary statistics will be provided for safety and efficacy endpoints, without formal hypothesis testing.

Sample Size Consideration:

A maximum sample size of 240 participants will be enrolled in the study including approximately 60 participants in Part 1 dose escalation and up to 180 participants in Part 2 dose expansion.

Approximately 60 participants will be enrolled in the Part 1 dose escalation portion of the study, including approximately 30 participants in Part 1A and 30 participants in Part 1B. The actual number of participants enrolled in Part 1 will depend on the tolerability of PF-07265028 as monotherapy and in combination with sasanlimab and the number of dose levels required to identify the MTD/MAD or RDE.

In Part 2A for combination therapy (4 cohorts in total), up to 40 participants will be enrolled for each expansion cohort. If the expansion cohort as monotherapy is explored based on emerging clinical, safety, PK, or PD data, then 20 additional participants will be enrolled for Part 2B. The sample size is based on practical consideration that the stated sample size will provide sufficient evidence of preliminary efficacy of PF-07265028 alone and in combination with sasanlimab. For an expansion cohort in Part 2A, for example, if minimal or no anti tumor activity is observed in the first 15 participants in each cohort, the enrollment for that cohort may be discontinued.

CCI

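### The weighted-DLT likelihood does not match its weight description for equivocal AEs that are non-DLTs by protocol: it enters each as a half-precision DLT, which can lower the admissible dose near the 25% limit

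*Protocol*

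**What the plan says.** Protocol Section 10.11.3 sets up the weighted analysis as follows: "Suppose n participants treated at dose d with m unequivocal DLTs and r equivocal DLTs/AEs, and the weight w for the equivocal data". The posterior is then proportional to the prior times `p^m (1−p)^(n−r−m) p^(rw)`. The section calls this a power-prior construction and describes w as a precision parameter for the equivocal data.

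The same section explains the weights by type of event. An equivocal DLT goes down, for example from 1 to 0.5. For the other type, "the weight for an equivocal AE (non-DLT by protocol) is increased (eg, 0 increased to 0.5". On the value used: "To maintain the integrity of a trial, the weight is pre-specified as 0.5 in the analysis".

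The weighted analysis is a sensitivity analysis, but it can be promoted. If all investigators and the sponsor agree on the equivocal data, SAP Section 5.1 says that "the DLT weighting approach could be the primary dose escalation method". Protocol Sections 9.3.2 and 10.11.3 say the same.

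**The concern.** The weight description starts each event at its protocol coding, 1 for a DLT and 0 for a non-DLT, and moves both to 0.5. A likelihood that implements this should return the ordinary model at both ends of the scale. The printed one does so only at 1.

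For an AE that is not a DLT by protocol, moving to 0.5 adds half an event, as described, and also deletes a whole non-event, which is not described. Both types are pooled in one count r, so the formula cannot treat them differently.

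At stake is the posterior overdose probability that is compared with the 25% limit. If the weighted model is made primary, a dose could be closed, or an escalation withheld, because of how protocol non-events are entered.

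**Working it through.** **Inputs.** All are from the Protocol.
- Section 10.11.1: logit p(d) = log α + β log(d/600). The reference dose is 600 "mg QD and used to scale the doses of PF-07265028".
- Section 10.11.2: "It was assumed based on pre-clinical data that DLT rate at 600 mg QD dose was 0.2", so the prior mean of log α is logit(0.2) = −1.386. The prior mean of log β is 0, the SDs are 2 and 1, and the correlation is 0.
- Section 10.11.3: w = 0.5.
- Section 9.3.2: a dose is open if P(p ≥ 0.33) is below 25%.

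**Reproducing the plan's figures.** Integrating this prior on a fine two-dimensional grid gives these overdose probabilities:

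| Dose (mg) | 25 | 50 | 80 | 125 | 200 | 320 | 500 |
|---|---|---|---|---|---|---|---|
| Recomputed | 0.071 | 0.092 | 0.112 | 0.137 | 0.174 | 0.230 | 0.316 |
| Table 16 | 0.071 | 0.091 | 0.109 | 0.135 | 0.171 | 0.230 | 0.317 |

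The largest difference is 0.003, so the model is the plan's.

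**Algebra.** Compare two forms:
- Printed: `p^(m+rw) (1−p)^(n−r−m)`
- Fractional-event: `p^(m+rw) (1−p)^(n−m−rw)`

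| Weight | Printed | Fractional-event |
|---|---|---|
| w = 1 | p^(m+r) (1−p)^(n−m−r), ordinary model with r DLTs | the same |
| w = 0 | p^m (1−p)^(n−m−r), the r participants are dropped | p^m (1−p)^(n−m), ordinary model with r non-DLTs |
| w = 0.5, per equivocal participant | half an event, no non-event | half an event, half a non-event |

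The w = 0 row is a check of the formula; that weight is not run. As an illustration, take 25 mg, n = 3, 1 DLT and 1 equivocal AE. The printed form at w = 0 gives an overdose probability of 0.357 at 25 mg. Coding the AE as a non-DLT gives 0.232.

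**Effect at w = 0.5.** The data are assumed, with 0/3 at every lower dose. The Data columns show events + non-events at the current dose. The last two columns are P(overdose).

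| Current dose; DLT + equivocal of n | Data, printed | Data, fractional | Assessed at | Printed | Fractional |
|---|---|---|---|---|---|
| 25 mg; 0 + 2 of 3 | 1 + 1 | 1 + 2 | 25 mg | 0.357 | 0.232 |
| 25 mg; 0 + 3 of 6 | 1.5 + 3 | 1.5 + 4.5 | 25 mg | 0.270 | 0.159 |
| 80 mg; 1 + 1 of 3 | 1.5 + 1 | 1.5 + 1.5 | 125 mg | 0.253 | 0.225 |
| 125 mg; 1 + 1 of 3 | 1.5 + 1 | 1.5 + 1.5 | 200 mg | 0.257 | 0.232 |
| 25 mg; 0 + 1 of 3 | 0.5 + 2 | 0.5 + 2.5 | 50 mg | 0.156 | 0.128 |

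The first four rows cross 25%; the fifth does not. In the first two, the starting dose fails the limit with no unequivocal DLT.

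**How often.** The grid took current doses of 25 to 200 mg, 0/3 at each lower dose, n = 3 to 6, m = 0 to 2 and r = 1 or 2 (with m + r ≤ n), and allowed at most one step up. The highest admissible dose differed in 17 of 115 scenarios (17/115 = 15%). The printed form gave the lower dose in all 17. The other 98 were unchanged.

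**The case against.** The strongest defence is that Section 10.11.3 says what w is. It is a precision parameter in a power prior, and a power prior at w = 0 discards data; it does not convert an event into a non-event. Half an event out of half a participant is then what reduced precision means, and the fractional-event form used as comparator appears nowhere in the documents.

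This stands for equivocal DLTs. Their protocol outcome is an event, discounting it is coherent, and the printed form lowers risk against full counting. At 25 mg with 2 equivocal of 3 it gives 0.357, against 0.674 if both are full DLTs. It does not stand for AEs that are non-DLTs by protocol. Their protocol outcome is a non-event, so a discount would shrink a factor (1−p). The printed form replaces that factor with a discounted p, and the weight description does not say so.

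The mitigations also stand. The analysis is secondary unless promoted, and dosing decisions are joint. Protocol Section 4.3.2 lets a threshold of, for example, 30% be considered after safety review. At 30%, the cases at 0.253, 0.257 and 0.270 no longer fail; the case at 0.357 still does.

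A reader might infer that participants will vanish from the planned analysis. The documents do not support this, because the weight is fixed at 0.5.

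**Conclusion.** The formula and the weight description in Section 10.11.3 conflict for equivocal AEs that are non-DLTs by protocol, and should be reconciled. That part is exact algebra and needs no assumption.

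The effect on decisions is real but limited to near-threshold data, and it runs toward lower doses. The cost is a dose wrongly closed or an escalation withheld, not added toxicity. It matters most if the weighted method becomes primary.

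It is tempting to say that the weighted model overstates DLT risk in general. The documents do not support that. The excess is relative to fractional-event counting and concerns mainly protocol non-DLTs; for equivocal DLTs the printed form reduces risk against full counting.

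The sizes rest on assumed cohort data, the Part 1A model only, and a comparator chosen because it meets the plan's own endpoints of 0 and 1. The 15% is a share of a constructed grid, not a probability of occurrence. The Technical Supplement, which holds the plan's scenarios and operating characteristics, was not available.

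**What to change.** Replace the likelihood in Protocol Section 10.11.3 with `p^(m+rw) (1−p)^(n−m−rw)`, keeping w = 0.5, at least for equivocal AEs that are non-DLTs by protocol. Then re-run the Technical Supplement scenarios.

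If the power-prior discount is to be kept for equivocal DLTs, split r into equivocal DLTs (r1) and equivocal protocol non-DLTs (r2) and use `p^(m + w·r1 + w·r2) (1−p)^(n − m − r1 − w·r2)`. An r1 participant then contributes p^w, and an r2 participant p^w (1−p)^(1−w). At w = 0 the latter is an ordinary non-DLT.

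In either case, align the description of weights 0 and 1 with the formula. If the sponsor does intend protocol non-DLTs to enter as discounted DLTs, the text should say so and drop the statement that their weight rises from 0.

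The cost is one exponent (or one extra count) in the appendix and code, plus the re-run. The weighted model becomes slightly less conservative.

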10.12. Appendix 12: RECIST (Response Evaluation Criteria In Solid Tumors) version 1.1 Guidelines

Adapted from Eisenhauer EA, et al (2009).⁵⁴

CATEGORIZING LESIONS AT BASELINE

Measurable Lesions

Lesions that can be accurately measured in at least 1 dimension.

- Lesions with longest diameter twice the slice thickness and at least 10 mm or greater when assessed by CT or MRI (slice thickness 5-8 mm).
- Lesions with longest diameter at least 20 mm when assessed by Chest X-ray.
- Superficial lesions with longest diameter 10 mm or greater when assessed by caliper.
- Malignant lymph nodes with the short axis 15 mm or greater when assessed by CT.

NOTE: The shortest axis is used as the diameter for malignant lymph nodes, longest axis for all other measurable lesions.

Non-measurable disease

Non-measurable disease includes lesions too small to be considered measurable (including nodes with short axis between 10 and 14.9 mm) and truly non-measurable disease such as pleural or pericardial effusions, ascites, inflammatory breast disease, leptomeningeal disease, lymphangitic involvement of skin or lung, clinical lesions that cannot be accurately measured with calipers, abdominal masses identified by physical exam that are not measurable by reproducible imaging techniques.

- Bone disease: Bone disease is non-measurable with the exception of soft tissue components that can be evaluated by CT or MRI and meet the definition of measurability at baseline.
- Previous local treatment: A previously irradiated lesion (or lesion subjected to other local treatment) is non-measurable unless it has progressed since completion of treatment.

Normal sites

- Cystic lesions: Simple cysts should not be considered as malignant lesions and should not be recorded either as target or non-target disease. Cystic lesions thought to represent cystic metastases can be measurable lesions if they meet the specific definition above. If non-cystic lesions are also present, these are preferred as target lesions.

- Normal nodes: Nodes with short axis <10 mm are considered normal and should not be recorded or followed either as measurable or non-measurable disease.

RECORDING TUMOR ASSESSMENTS

All sites of disease must be assessed at baseline. Baseline assessments should be done as close as possible prior to study start. For an adequate baseline assessment, all required scans must be done within 28 days prior to treatment and all disease must be documented appropriately. If baseline assessment is inadequate, subsequent statuses generally should be indeterminate.

Target lesions

All measurable lesions up to a maximum of 2 lesions per organ, 5 lesions in total, representative of all involved organs, should be identified as target lesions at baseline. Target lesions should be selected on the basis of size (longest lesions) and suitability for accurate repeated measurements. Record the longest diameter for each lesion, except in the case of pathological lymph nodes for which the short axis should be recorded. The sum of the diameters (longest for non-nodal lesions, short axis for nodal lesions) for all target lesions at baseline will be the basis for comparison to assessments performed on study.

- If 2 target lesions coalesce the measurement of the coalesced mass is used. If a large target lesion splits, the sum of the parts is used.
- Measurements for target lesions that become small should continue to be recorded. If a target lesion becomes too small to measure, 0 mm should be recorded if the lesion is considered to have disappeared; otherwise a default value of 5 mm should be recorded.

NOTE: When nodal lesions decrease to <10 mm (normal), the actual measurement should still be recorded.

Non-target disease

All non-measurable disease is non-target. All measurable lesions not identified as target lesions are also included as non-target disease. Measurements are not required but rather assessments will be expressed as ABSENT, INDETERMINATE, PRESENT/NOT INCREASED, INCREASED. Multiple non-target lesions in 1 organ may be recorded as a single item on the CRF (eg, 'multiple enlarged pelvic lymph nodes' or 'multiple liver metastases').

OBJECTIVE RESPONSE STATUS AT EACH EVALUATION (SEE Table 17)

Disease sites must be assessed using the same technique as baseline, including consistent administration of contrast and timing of scanning. If a change needs to be made the case must be discussed with the radiologist to determine if substitution is possible. If not, subsequent objective statuses are indeterminate.

Target disease

- Complete response: Complete disappearance of all target lesions with the exception of nodal disease. All target nodes must decrease to normal size (short axis <10 mm). All target lesions must be assessed.
- Partial response: Greater than or equal to 30% decrease under baseline of the sum of diameters of all target measurable lesions. The short diameter is used in the sum for target nodes, while the longest diameter is used in the sum for all other target lesions. All target lesions must be assessed.
- Stable: Does not qualify for CR, PR, or progression. All target lesions must be assessed. Stable can follow PR only in the rare case that the sum increases by less than 20% from the nadir, but enough that a previously documented 30% decrease no longer holds.
- Objective progression: 20% increase in the sum of diameters of target measurable lesions above the smallest sum observed (over baseline if no decrease in the sum is observed during therapy), with a minimum absolute increase of 5 mm.
- Indeterminate: Progression has not been documented, and:
 - 1 or more target measurable lesions have not been assessed.
 - or assessment methods used were inconsistent with those used at baseline.
 - or 1 or more target lesions cannot be measured accurately (eg, poorly visible unless due to being too small to measure).
 - or 1 or more target lesions were excised or irradiated and have not reappeared or increased.

Non-target disease

- CR: Disappearance of all non-target lesions and normalization of tumor marker levels. All lymph nodes must be 'normal' in size (<10 mm short axis).
- Non-CR/Non-PD: Persistence of any non-target lesions and/or tumor marker level above the normal limits.

- **PD: Unequivocal progression of pre-existing lesions.** Generally the overall tumor burden must increase sufficiently to merit discontinuation of therapy. In the presence of SD or PR in target disease, progression due to unequivocal increase in non-target disease should be rare.
- **Indeterminate:** Progression has not been determined and 1 or more non-target sites were not assessed or assessment methods were inconsistent with those used at baseline.

New Lesions

The appearance of any new unequivocal malignant lesion indicates PD. If a new lesion is equivocal, for example due to its small size, continued assessment will clarify the etiology. If repeat assessments confirm the lesion, then progression should be recorded on the date of the initial assessment. A lesion identified in an area not previously scanned will be considered a new lesion.

Supplemental Investigations

- If CR determination depends on a residual lesion that decreased in size but did not disappear completely, it is recommended the residual lesion be investigated with biopsy or fine needle aspirate. If no disease is identified, objective status is CR.
- If progression determination depends on a lesion with an increase possibly due to necrosis, the lesion may be investigated with biopsy or fine needle aspirate to clarify status.

Subjective progression

Participants requiring discontinuation of treatment without objective evidence of disease progression should not be reported as PD on tumor assessment CRFs. This should be indicated on the EOT CRF as off treatment due to Global Deterioration of Health Status. Every effort should be made to document objective progression even after discontinuation of treatment.

Table 17. Objective Response Status at Each Evaluation

Target Lesions	Non-target Disease	New Lesions	Objective status
CR	CR	No	CR
CR	Non-CR/Non-PD	No	PR
CR	Indeterminate or Missing	No	PR
PR	Non-CR/Non-PD, Indeterminate, or Missing	No	PR
SD	Non-CR/Non-PD, Indeterminate, or Missing	No	Stable
Indeterminate or Missing	Non-PD	No	Indeterminate
PD	Any	Yes or No	PD
Any	PD	Yes or No	PD
Any	Any	Yes	PD

If the protocol allows enrollment of participants with only non-target disease, the following Table 18 will be used:

Table 18 Objective Response Status at each Evaluation for Patients with Non-Target Disease Only

Non-target Disease	New Lesions	Objective status
CR	No	CR
Non-CR/Non-PD	No	Non-CR/Non-PD
Indeterminate	No	Indeterminate
Unequivocal progression	Yes or No	PD
Any	Yes	PD

090177e198aafefApproved\Approved On: 22-Nov-2021 20:52 (GMT)

